### 3. SCHEDULE OF ACTIVITIES (SOA)

The Table of Measures shows the assessment measures in column 1 and the part of the study during which these measures are made in the remaining columns. Additionally, participants will complete the Credibility/ Expectancy Questionnaire (CEQ) each time that they start one of the study interventions. All study participants will complete the CEQ when they start EMM, all randomized participants will complete the CEQ when they start BIO or INJ as a randomized treatment, and participants will complete the CEQ if they select BIO, INJ or SNS when they are identified as non-responders to the randomized treatment at the 3-month follow-up assessment.

#### Table of Measures for all participants

Schedule of assessments*	Screening Baseline Randomi		Randomize	3 mo	6 mo	12 mo	18 mo	24 mo
Socio-demographics and examination	Х							
Bowel diary, including BSFS		х	х	х	Х	х		Х
Endoanal ultrasound		X**		X*** (INJ arm only)				
Balloon Evacuation Test (BET)		X**						
Anorectal manometry (ARM)		X**		X***				
Magnetic Evoked Potential (MEP)		X**		X***				
Fecal Incontinence Severity Scale (FISS)		X	x	х	X	X		X
Fecal Incontinence Quality of Life (FIQOL)		Х	x	x	Х	X		X
PHQ-12 Somatization scale			x	Х	X	Х		Х
PROMIS Anxiety-7			Х	Х	X	Х		Х
PROMIS Depression-8			X	Х	X	Х		Х
PROMIS Self-Efficacy Symptom Management			x	х	X	Х		X
Assessment of AEs, SAEs		Х	x	х	X	X	х	х
Cost (treatments, # of visits, out of pocket)		X	x	х	X	x	X	X
Work Productivity and Impairment (WPAI)		X	x	х	X	x	X	X
EuroQol 5D (EQ-5D)		X	X	Х	X	Х	Х	Х
Burden of Treatment Questionnaire		X	x	x	X	x	x	X
GI Symptom Questionnaire		X						
ABLe	3 		X	Х	X	Х		X
Continence Rating			х	Х	X	Х		Х

\* Additionally, participants will complete the Credibility/ Expectancy Questionnaire (CEQ) each time that they start one of the study interventions. So, all study participants will complete the CEQ when they start EMM all randomized participants will complete the CEQ when they start BIO or INJ as a randomized treatment, and participants will complete the CEQ if they select BIO, INJ or SNS when they are identified as non-responders to the randomized treatment at the 3-month follow-up assessments.

\*\* The endoanal ultrasound, BET, ARM and MEP may be conducted at the randomization visit, if not done at Baseline but must be conducted prior to randomization. If an imaging study (US or MRI) was performed in the previous 12 months to assess the sphincters, then this need not be repeated at Baseline if the sphincters appeared normal and there has been no history of anorectal trauma, surgical procedures, or vaginal deliveries in the intervening period between the imaging exam and study participation.

\*\*\* The endoanal ultrasound (INJ only), the ARM (all participants) and the MEP (all participants) may be performed at the 3-month follow-up assessment. Participants who complete two 3-month follow-up visits should only have the ARM and MEP performed at the first 3-month follow-up visit. This will only apply to participants who initially respond to EMM but are later identified as non-responders at the 3-month follow-up visit and are then randomized to BIO or INJ. They will complete another 3-month follow-up visit, this time three months after they have initiated one of the randomized treatments. NOTE: Participants who elect to receive INJ as an optional treatment may have an endoanal ultrasound at their follow-up visit following completion of that treatment (likely their 6-month follow-up visit).

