who respond to the nonspecific treatment components that are included in the EMM protocol may make it easier to detect differential effects of BIO and INJ. Patients who are responders to EMM will be followed up 3 months later; those who remain responders will be continued on EMM and be followed for the remaining 24 months of the study. However, those who are no longer responders to EMM after 3 months will be invited to be randomized to BIO or INJ just like patients who failed EMM at the end of the initial run-in treatment, and all outcome measures will be assessed at 3 months from initiation of the treatment arm to which they are randomized. They will be pooled with other patients randomly assigned to the same treatment for the primary analyses and will be assessed at 6 months. Those subjects will participate for 27 months.

- 3. *Randomly assigned treatment:* The window for treatment to be initiated is 0 days 4 weeks after randomization. Based on a randomization scheme implemented by the Data Coordinating Center, each patient will be randomly assigned to BIO or INJ and treated as follows:
  - BIO will consist of 5 required one-hour training sessions which should, ideally, be spaced at weekly intervals; however, the window between visits is 2 10 days to accommodate participants' schedules as long as no more than two visits occur in one calendar week. A 6th treatment session will be made available for patients if it is shown through anorectal manometry that they are having trouble understanding directions given during the first five sessions. These will occur in the 5-6 or so weeks following the initiation of treatment. Treatment approaches will include strength training in all patients, sensory training for patients with hyposensitivity, and/or urge-resistance training for patients with hypersensitivity to the sensations caused by rectal distention. Home exercises will be assigned to patients to practice these skills, and these will be guided by a brochure.

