4.3.6 Anorectal manometry. Determine anal resting and anal squeeze pressures, sphincter squeeze endurance, rectal sensory thresholds (bag volume and intra-bag pressure at the first report of sensation, desire to defecate, urgency to defecate, and maximum tolerable volume), and rectal compliance. These parameters will be measured at baseline (but can be measured prior to randomization if not measured at Baseline) and may also be done at 3 months following initial treatment using the portable Medspira Anorectal manometry equipment, which can be used in the office and does not require a dedicated laboratory. This system includes a catheter, with 4 radially-oriented equidistant anal balloons and 1 rectal balloon, a wireless manometer, and a computer. The catheter is connected to the manometer that has pressure transducers and communicates wirelessly to the computer. The acquisition module display provides instructions that guide users conducting the study. The maneuvers used during portable manometry are identical to those in high-resolution manometry (HRM). Anorectal pressures and rectal sensation measured with portable manometry are significantly correlated with high-resolution manometry. Participants who initially respond to EMM but are then randomized after they are identified as non-responders at the 3-month follow-up visit may have the ARM performed at the initial 3-month assessment but it should not be repeated at their second 3-month follow-up assessment if they are then randomized to BIO or INJ.

4.3.7 Motor evoked potentials (MEP) will be tested at the Baseline visit (but can be tested at any time before randomization). It may also be tested at 3-month follow-up in all treatment groups. However, participants who initially respond to EMM but are then randomized after they are identified as non-responders at the 3-month follow-up assessment will not have the MEP repeated at their second 3-month follow-up assessment, that is, at the follow-up 3 months after they initiated the randomized treatment. The MEP data will be collected at the Mayo Clinic and Augusta University. MEP data will not be collected at the University of North Carolina at Chapel Hill, the University of Alabama at Birmingham, and the University of Michigan.

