#### 8.3 Analysis of Secondary Aims

*Identify predictors of treatment response to each intervention.* Generalized linear modeling will be used to identify baseline variables which are significant independent predictors of responder status at 3 months. Candidate independent variables in these models include (a) demographic variables (e.g., sex, age, race, ethnicity, education); (b) clinical history variables (e.g., FI frequency, volume, duration, and association with urgency and diarrhea); and (c) baseline pelvic floor physiology (e.g., anal canal resting pressure, squeeze pressure, duration of squeeze, rectal sensory threshold for first sensation and urgency, maximum tolerable volume, structural integrity of anal sphincters assessed by ultrasound, and integrity of the pelvic floor innervation by trans-sacral and trans-lumbar magnetic evoked potentials) and other moderator variables described in the protocol. Differences in predictors of response among the treatment groups will be assessed by evaluating interaction terms for the predictors and treatment group. Secondary analyses evaluating predictors of treatment response at other time points and predictors of other secondary outcomes will be conducted using similar methods.

Investigate the mechanistic basis for treatment success for each intervention. General linear modeling will be used to identify measures associated with change from baseline to 3 months in FI frequency. The independent variables to be tested are anal squeeze pressures, rectal sensory thresholds, rectal maximum tolerable volume, trans-lumbar and trans-anal magnetic evoked potential, stool consistency measure by the Bristol Stool Form Scale, and adherence to protocol. Differences in predictors among the treatment groups will be assessed by evaluating interaction terms for the predictors and treatment group.

*Evaluate treatment combinations.* To assess the effectiveness of allowing non-responders to choose an additional treatment at 3 months, we will estimate 95% confidence intervals for the number of responders in each treatment-order combination at 6, 12, and 24 months using a Wilson Score interval. Confidence intervals will be compared descriptively.

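### EMM responders who relapse and are then randomized may have follow-up manometry and MEP only before BIO or INJ, so by rule they contribute no post-treatment physiology to the mechanistic aim

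*Combined protocol and SAP*

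**What the plan says.** The Table of Measures schedules ARM and MEP at Baseline and, as an option, at 3 months. It schedules neither test later. The first test may be delayed "if not done at Baseline but must be conducted prior to randomization", so every randomized participant should have one measurement before BIO or INJ.

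The footnote to that table, repeated under Table 2, sets a special rule for anyone with two 3-month visits: they "should only have the ARM and MEP performed at the first 3-month follow-up visit". On who is covered it says: "This will only apply to participants who initially respond to EMM but are later identified as non-responders at the 3-month follow-up visit" and who are then randomized. On the later visit it says: "They will complete another 3-month follow-up visit, this time three months after they have initiated one of the randomized treatments".

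The measurement sections agree. Section 4.3.6 allows ARM at the first 3-month assessment and says "it should not be repeated at their second 3-month follow-up assessment if they are then randomized to BIO or INJ". Section 4.3.7 says these participants "will not have the MEP repeated at their second 3-month follow-up assessment".

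Section 3.0, item 2, says of the same participants: "They will be pooled with other patients randomly assigned to the same treatment for the primary analyses". Section 8.3 contains an analysis headed "Investigate the mechanistic basis for treatment success for each intervention". It models the change in FI frequency from baseline to 3 months on squeeze pressure, rectal sensory thresholds, maximum tolerable volume, MEP, stool consistency and adherence.

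**The concern.** For these participants the first 3-month visit follows EMM alone, and the second is the only 3-month visit after BIO or INJ. The rule places the single permitted follow-up test before the treatment whose mechanism is under study and forbids it afterwards.

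The mechanistic question is a stated purpose of the trial (Aim C; Section 2.3, objective 3). Section 2.2.1 notes that the relation between symptom improvement and anorectal function after BIO has not been evaluated. Section 2.2.2 says that the mechanism of dextranomer is unknown. Answering either question calls for physiology measured after treatment, ideally as a change from a pre-treatment value. The rule rules this out for one identifiable subgroup. That subgroup consists of people who first responded to EMM, so the gap is not random with respect to patient type.

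There is also a labelling hazard. A relapser who is randomized can hold an ARM/MEP record from a 3-month visit that was taken before treatment, alongside a 3-month FI outcome taken after it.

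**Working it through.** **Step 1: order of events.**

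| | Randomized straight after EMM | EMM responder, relapses, then randomized |
|---|---|---|
| ARM/MEP at Baseline or before randomization | yes | yes |
| 3-month visit after EMM alone | none | first 3-month visit: ARM/MEP optional |
| 3-month visit after BIO or INJ starts | ARM/MEP optional | second 3-month visit: ARM/MEP barred |
| ARM/MEP at 6, 12, 18 or 24 months | not scheduled | not scheduled |

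The right-hand column has no scheduled ARM or MEP after BIO or INJ. The footnotes to both schedule tables and Sections 4.3.6 and 4.3.7 all give the same rule, so this is not a wording slip in one place.

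**Step 2: could other data fill the gap?** Section 6.2 describes a brief manometry at the start of each BIO session. It guides the therapist, is not listed as an outcome measure, is done before that day's training, and has no counterpart in the INJ arm. It cannot replace the 3-month test.

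**Step 3: the plan's own flow.** Inputs from Section 5.4: 285 start EMM, 15% attrition, 20% EMM responders (given as 57), 194 randomized.
- 285 × 0.85 × 0.80 = 193.8, which reproduces 194. On this route the EMM responders number 285 × 0.85 × 0.20 = 48.45, about 48.
- The stated 57 is 285 × 0.20. Subtracting it gives 285 − 42.75 − 57 = 185.25, which does not reproduce 194.

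I therefore carry both 48 and 57 as the number of EMM responders.

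**Step 4: size of the affected group.** The documents give no relapse rate, so r, the fraction of EMM responders who relapse by 3 months and are randomized, is an assumption. Number affected = responders × r; share = number ÷ 194.

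| r | from 48 responders | from 57 responders |
|---|---|---|
| 10% | 4.8 (2.5%) | 5.7 (2.9%) |
| 25% | 12.0 (6.2%) | 14.25 (7.3%) |
| 50% | 24.0 (12.4%) | 28.5 (14.7%) |
| 100% (ceiling) | 48 (24.7%) | 57 (29.4%) |

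Over r = 10% to 50% this is about 5 to 29 people; 5 ÷ 194 = 2.6% and 29 ÷ 194 = 14.9%. These counts are people covered by the rule. The number who would actually have had a follow-up test is smaller, because the test is optional. It is smaller again for MEP, which Section 4.3.7 confines to two of the five sites.

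**Step 5: which values does Section 8.3 use?** The predictor analysis specifies baseline pelvic floor physiology. The mechanistic analysis drops the word baseline and includes adherence, which arises after baseline, but it does not say whether physiology enters as a baseline, 3-month or change value. If baseline values are meant, this subgroup loses nothing. If 3-month or change values are meant, it cannot contribute.

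**The case against.** The strongest reply is that the harm depends on something the plan does not state. Section 4.3 lists ARM and MEP among moderator variables, the synopsis uses them to subtype the physiological basis of FI, and Aim C names baseline physiology among the predictors. On a baseline-only reading of Section 8.3 nothing is lost. That stands as a condition on the point. Against it, a mechanistic analysis confined to baseline physiology would largely repeat the predictor analysis beside it, and it would leave the optional 3-month test without a stated use.

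Second, follow-up physiology will be patchy in both arms: testing is optional, the 3-month assessment may be remote, and MEP is done at two sites. This is true, and the subgroup is only part of the incompleteness. But elsewhere the test may be missed; here it is forbidden.

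Third, the rule is deliberate: the version 3.0 entry in the change log records it. That entry gives no reason for choosing the first visit over the second. If the aim was to limit burden, one test at the second visit meets it equally well.

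Fourth, post-EMM physiology in relapsers might serve the EMM predictor analysis, since Section 8.3 mentions predictors of EMM response at several time points. Aim E frames that analysis as patient characteristics that predict response, and no stated analysis requires manometry repeated after EMM. This remains a real but small cost of moving the test.

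A reader might infer more than the documents support:
- That these participants have no physiology apart from the first 3-month visit. They also have the Baseline or pre-randomization test.
- That the mechanistic associations will be biased towards zero. That would require an analyst to use the first-visit record as the post-treatment value. Nothing in the plan prescribes this, Section 3.1 resets the timeline when the randomized treatment starts, and the pooling sentence in Section 3.0 concerns the primary analyses.

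**Conclusion.** The point holds in a limited form. For EMM responders who relapse and are randomized, the protocol permits follow-up ARM/MEP only before BIO or INJ and bars it afterwards, so all their scheduled physiology is pre-treatment. No other randomized participants are excluded by rule from post-treatment or change-in-physiology analyses.

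The size rests on an assumed relapse-and-randomize rate. At 10% to 50% of 48 to 57 EMM responders it is roughly 5 to 29 of 194, about 3% to 15%, and fewer for MEP. The practical loss is conditional on Section 8.3 using 3-month or change values. The primary efficacy, safety and cost analyses and the sample size are unaffected. This is an inexpensive improvement to a secondary aim, not a threat to the trial's main conclusions.

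**What to change.** 1. For EMM responders who relapse and are randomized, move the single optional ARM/MEP from the first to the second 3-month visit.
2. At the first 3-month visit, enter the diary and obtain the EDC response classification (Section 4.1.1) before any ARM/MEP. Do the test at that visit only if the participant is not going on to randomization.
3. Label any first-visit test already done in these participants as pre-treatment, and do not use it as the value after BIO or INJ.
4. State in Section 8.3 that the mechanistic model uses change in physiology from pre-treatment to 3 months after treatment starts. Where a participant has two pre-treatment tests, name in advance which one is the reference.
5. Align the footnotes to the Table of Measures and Table 2 with Sections 4.3.6 and 4.3.7.

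The cost is protocol wording, an EDC label and one sentence in the analysis section. The maximum number of tests per participant does not change. Two things are given up: post-EMM physiology in relapsers who are randomized, and some flexibility at the first 3-month visit, because the paper diary must be entered before the test can be done.

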### 1.0 Study Overview

Fecal incontinence (FI) is very common: 3% of US adults report that it occurs at least weekly. It often has a devastating impact on quality of life and may lead to premature admission to a nursing home. In August 2013, the National Institute of Diabetes, Digestive and Kidney Diseases (NIDDK) invited leaders in the field to a workshop to develop a clinical research agenda for FI. Overwhelmingly, participants identified biofeedback, sacral nerve electrical stimulation, and perianal injection of an inert bulking agent as potentially useful treatments but felt that a critical barrier to progress is the lack of consistent evidence from well-designed, randomized controlled trials (RCTs) regarding their efficacy. The workshop identified trials comparing the effectiveness, safety, and costs of these treatments as the highest priority for research funding. Our goal is to address this significant gap in knowledge by conducting a multisite study comparing the effectiveness, safety, and costs of these treatment (FIT) study, approximately 285 people with moderate to severe FI will be enrolled in this multi-site study. All participants will first be treated with 4 weeks of Enhanced Medical Management (EMM), and 194 who do not respond to EMM will be randomized to the two interventions, Biofeedback (BIO) or injections of Dextranomer bulking agent (INJ). Three months thereafter, non-responders (less than a 75% reduction in FI episodes) may choose to undergo a different (i.e., a second) intervention from the 3 options of BIO, INJ, or Sacral Nerve Stimulation (SNS).

Our specific aims are as follows:

### 1.1 Specific Aims

- A. Compare the effectiveness, safety, and cost of two treatments for moderate to severe FI in 194 male and female patients in a multi-center RCT; the interventions are biofeedback therapy (5 required weekly sessions with the option of an additional 6th visit, as needed) and perianal injection of the inert bulking agent dextranomer (INJ; Solesta). A ≥75% reduction in average weekly FI episodes compared to baseline will define a responder. The primary efficacy analysis will occur 3 months following the start of each treatment, with long-term follow-up through 2 years. Secondary outcomes will include a validated FI severity scale, a disease-specific quality of life scale, and measures of psychological distress.
  - Research objective 1 (primary). For the primary test of efficacy, the null hypothesis is that the proportion of responders in the two treatment groups will not be different. Secondary analyses will test for equivalence at other time points (e.g., 6, 12 and 24 months follow up) and will compare treatment groups on other secondary outcome measures.
  - Research objective 2 (primary). For the primary test of safety, the null hypothesis is that at 3 months follow up, the proportion of patients with adverse events (AEs) of pelvic pain of grade II or higher based on Common Terminology Criteria for AE (CTCAE) criteria, treatment site infection, or SAEs requiring hospitalization will not be different in the BIO or INJ groups. Secondary analyses will evaluate this outcome at 6, 12, 18, and 24 months follow up.
  - Research objective 3 (primary). At 3 months follow up, the estimated average cost for enhanced medical management non-responders will not be different for the two treatments. Secondary analyses will evaluate this outcome at 6, 12, 18, and 24 months.
- B. Compare efficacy in patients who complete all assigned treatment visits. Efficacy may be influenced by the number of BIO treatment sessions and the requirements to learn and practice new skills. Thus, in a secondary analysis, the primary efficacy outcome will be compared between treatment groups in the subset of participants who completed the treatment to which they were randomized.
- C. Identify baseline predictors of responsiveness to each intervention and the mechanistic basis for each treatment. Candidate predictors are (a) demographic variables (e.g., sex, age, race, ethnicity, education); (b) clinical history variables (e.g., FI frequency, volume, duration, and association with urgency and diarrhea); and (c) baseline pelvic floor physiology (e.g., anal canal resting pressure, squeeze pressure, duration of squeeze, rectal sensory threshold for first sensation and urgency, maximum tolerable volume, structural integrity of anal sphincters assessed by ultrasound, and integrity of the pelvic floor innervation by trans-sacral and trans-lumbar magnetic evoked potentials).

- D. Evaluate treatment combinations. Patients who do not meet the responder criterion by 3 months follow up will be offered the option of choosing additional therapy. This constitutes a pragmatic clinical trial which mimics clinical practice and will provide preliminary data for a future study. A second reason for allowing patients to add an additional preferred treatment if they do not show at least a 75% improvement is to facilitate recruitment; in our feasibility survey, subjects told us that the opportunity to try another treatment if the first failed would increase their willingness to be randomized. Data analysis will estimate 95% confidence intervals for the percent of responders to each treatment combination and to each monotherapy, and differences in responder rates between groups will be assessed.
  - Research objective 4. To compare the improvement in FI after combination treatment versus monotherapy and compare improvement among various treatment combinations, up to 24 months after administration of each treatment combination, compared to monotherapy.
  - Research objective 5. To estimate differences in the magnitude of improvement in FI from baseline to end of treatment between the treatment combinations.
- E. Assess the efficacy and durability of enhanced medical treatment and identify patient characteristics that predict treatment response.
  - Research objective 6. To estimate the responder rate during the last two weeks of enhanced medical treatment and also during follow up at 3, 6, 12, and 24 months.
  - Research objective 7. To assess the proportion of patients reporting AEs of pelvic pain of grade II or higher, or SAEs requiring hospitalization, during all weeks of medical treatment.
  - Research objective 8. To estimate the cost of delivering medical treatment and compare to the cost of delivering any of the other two treatments.
- F. Compare the cost effectiveness of two treatments for moderate to severe FI.
  - Research objective 9: To estimate the average cost effectiveness (i.e., cost per quality adjusted life year gained excluding costs that are only for research purposes) among conservative medical management non-responders for the two treatments at 6, 12, 18 and 24 months.

This 4-site geographically dispersed study will identify the most optimal, durable, safe, and inexpensive treatment for moderate to severe FI patients. In addition, this project will demonstrate the efficacy of enhanced medical management of FI, explore the mechanisms of action for the study treatments, and identify the factors that predict the response to treatment. A successful outcome may result in changes to management strategies.

